9.2.3.5. Exploratory analyses

Additional analyses may be performed, as necessary. Exploratory analyses will be reported only when results obtained provide an important interpretation.

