#### **8.7.2. Safety analyses**

Serious adverse events entered in the CRF submitted by the investigator for which the causal relationship with this product cannot be ruled out will be handled as serious adverse reactions, and the number and proportion of subjects with serious adverse reactions ([%]: number of patients with adverse reactions/number of subjects included in safety analysis) will be tabulated. Exploratory analyses will be performed as needed.

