3. INTERIM AND FINAL ANALYSES

In this study, interim analyses for Japan Periodic Safety Update Report (J-PSUR) will be conducted on a regular basis. Interim analyses for purposes other than J-PSUR will also be conducted, as necessary. At the time of an interim analysis, only necessary items selected from the full analysis items defined in this SAP will be analyzed. A final analysis will be conducted to support the application of reexamination. At the time of final analysis, the full items defined in this SAP will be analyzed.

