4. HYPOTHESES AND DECISION RULES

Because of the non-confirmatory nature of this study, no hypothesis tests will be performed in this study.

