5.4. Subgroups

Subgroup analyses of safety will be performed with respect to the following recipient characteristics (factors). The subgroups in each categorization are indicated in the squared brackets [] with the reference for risk ratio/difference being underlined.

- Sex [male, female]

- Age [<55 yrs., ≥55 yrs.], [<65 yrs., ≥65 yrs.]
- Past history of allergy [absent, present]

In addition, subgroup analyses of safety with respect to other factors indicated below will be performed, as necessary:

- Suspected pregnancy/Lactation (women only, for each dose number for initial immunization) [absent, present]
- Pregnancy (women only) [absent, present]
- Lactation (women only) [absent, present]
- History of other vaccination (except boosts) [absent, present]
- Renal impairment [absent, present]
- Hepatic impairment [absent, present]

Presence/absence of renal/hepatic impairment should be determined according to “Attachment: Procedure to Extract Patients with Hepatic/Renal Impairment in Post-Marketing Investigations”.

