9.1.3. Binary variables

For binary variables, subjects included in each binary category will be calculated in terms of frequency and proportion. When a confidence interval (CI) is determined for a proportion, the two-sided 95% CI (exact method) will be determined.

When a comparison for proportion is made between subgroups, the risk ratio and its 95% CI will be calculated. They will also be presented graphically (See Appendix 1).

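### Reporting of the unspecified exploratory analyses depends on their results, so a reader cannot judge how selected the exploratory part of the report is

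*SAP*

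**What the plan says.** SAP 9.2.3.5 has two sentences. The first opens the door: "Additional analyses may be performed, as necessary". The second sets the reporting rule: "Exploratory analyses will be reported only when results obtained provide an important interpretation". The section does not define what makes an interpretation important, and it names nobody to decide.

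Three other statements fix the setting:

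- SAP 4 rules out testing: "Because of the non-confirmatory nature of this study, no hypothesis tests will be performed in this study".
- SAP 9.1.3 gives the form of any subgroup comparison: "When a comparison for proportion is made between subgroups, the risk ratio and its 95% CI will be calculated".
- SAP 3 secures the prespecified content at the end of the study: "At the time of final analysis, the full items defined in this SAP will be analyzed".

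**The concern.** The condition in SAP 9.2.3.5 is the result itself. An exploratory analysis that was run and showed nothing of note may be left out, and the report need not say that it was run. What remains has been chosen for its result, and the reader has no denominator against which to weigh it.

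This matters more here than in a controlled trial. Protocol 8.9 notes that there is no control group, and with no hypothesis tests the plan has no multiplicity control. Knowing what was looked at is then the main means of weighing a post hoc result. Some questions of natural interest would also have to be exploratory: SAP 9.2.3.3 plans no subgroup comparison for COVID-19, and SAP 10 gives serious events after the booster as lists, with no comparison planned.

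The results have regulatory uses. SAP 3 ties the final analysis to the re-examination application. Protocol 13 ties the study to review of the risk management plan, and Protocol 15 to possible revision of the package insert. Both a chance finding shown without its context and a reassuring finding left out could mislead.

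**Working it through.** The plan states no alpha, power or number of exploratory analyses on this point, so there is no figure to reproduce. The check has two steps.

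**Step 1. Does anything elsewhere offset the rule?**

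| Place | What it provides | Does it require all exploratory analyses, or their number, to be reported? |
|---|---|---|
| Protocol 8.7.2 (safety) | Exploratory analyses as needed | No; silent on reporting |
| Protocol 8.7.3 (COVID-19) | The same | No; silent on reporting |
| SAP 3 | All items defined in the SAP are analysed at the final analysis | No; an unspecified analysis is not a defined item |
| SAP 10 | Listings of subjects, events and excluded data | No; no list of analyses performed |

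Nothing offsets it. SAP 3 does mark the limit of the problem. The outputs in SAP 9.2.3.1 to 9.2.3.4 (serious adverse reactions and events, onset time, VAED/VAERD, COVID-19, subgroups) and the listings in SAP 10 are defined items, so the rule in 9.2.3.5 does not reach them.

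**Step 2. Why the number of analyses matters (generic illustration).**

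Inputs: a 95% confidence level, from SAP 9.1.3; k comparisons, assumed because the documents give no number; independence and nominal coverage, also assumed; no true association.

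Formulas: P(at least one interval excludes the null) = 1 − 0.95^k; expected number of such intervals = 0.05 × k.

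| k (assumed) | 1 − 0.95^k | 0.05 × k |
|---|---|---|
| 1 | 1 − 0.9500 = 5.0% | 0.05 |
| 5 | 1 − 0.7738 = 22.6% | 0.25 |
| 10 | 1 − 0.5987 = 40.1% | 0.5 |
| 20 | 1 − 0.3585 = 64.2% | 1.0 |
| 40 | 1 − 0.1285 = 87.1% | 2.0 |

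The same reported interval means something different at k = 1 and at k = 40. Under SAP 9.2.3.5 the reader is not told which row applies.

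**The case against.** The strongest reply is that this is a descriptive study whose objectives are served by prespecified outputs, all required at the final analysis, and that the rule touches only extra work. That is correct, and it limits the point. It does not answer it, because an extra analysis that does reach the report still arrives without its context.

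Four stronger readings are tempting. The documents do not support them.

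- *The whole report is selected on results.* A reader might infer this from the wording of 9.2.3.5. SAP 3 allows items to be selected only at interim analyses and requires all defined items at the end.
- *An unreported signal would be invisible.* SAP 9.2.3 says that the listings cover all relevant events reported, and SAP 10 lists subjects with serious adverse events and reactions, including those after the booster. A cluster of events can still be seen, even if a particular cut of the data is not shown.
- *The pregnancy, lactation, renal and hepatic subgroups are optional.* SAP 5.4 does say that "subgroup analyses of safety with respect to other factors indicated below will be performed, as necessary". But SAP 9.2.3.4 calls for summaries by every factor in 5.4, and names pregnancy, renal impairment and hepatic impairment without condition for the tables by system organ class and preferred term. Together with SAP 3 this largely settles the matter. Lactation is covered only by the general phrase, so the wording of 5.4 is loose. It is still a condition on doing an analysis, not on its result, and so is not selective reporting.
- *The probabilities in the working measure the bias.* They do not. They describe multiplicity in general. The SAP does not equate importance with an interval that excludes the null, a reassuring null could count as important, and some exploratory outputs may be tables with no interval at all.

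**Conclusion.** The point holds for the exploratory part of the report. SAP 9.2.3.5 sets a rule, rather than leaving a gap, under which reporting is decided after the result is known. No other section requires the analyses run to be listed or counted. A reader therefore cannot judge how selected the reported exploratory results are.

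The size cannot be calculated from the documents. The range from 5.0% (k = 1) to 87.1% (k = 40) shows only why the number matters. It rests on an assumed k, independence, nominal coverage and no true association, and with few events coverage may differ from nominal.

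This is a transparency defect that should be corrected. It does not alter any stated figure, and it does not weaken the prespecified safety, COVID-19 or subgroup results.

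**What to change.** Replace the second sentence of SAP 9.2.3.5 with:

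> Every exploratory analysis performed will be listed in the study report, marked post hoc, with its reason, method and result (estimate and 95% CI where one is calculated); none will be omitted because of its result.

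The words in parentheses matter, because a purely descriptive table or listing has no estimate to give.

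SAP 5.4 and Protocol 8.7.2 need no change for this point. The cost is one sentence and a few more report pages, with no new data. If the SAP is not reopened, the same list can be put in the final study report, whose date Protocol 5 gives as still to be determined.

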10. LISTINGS

Tabulated lists will be presented for the following subjects or items:

- Subjects included in the study

In addition, separated lists will be presented for the following subjects included in the study:

- Elderly (≥65 yrs.)
- Subjects reported as “present” for pregnancy
- Subjects reported as “present” for renal impairment
- Subjects reported as “present” for hepatic impairment
- Subjects who experienced VAED or VAERD (See Section 9.2.3.2.3)

- Subjects who received one dose of vaccination for initial immunization during the study period of the Investigation of Health Status of Recipients Vaccinated First and received the second dose (regardless of whether it is with this product or not) during the observation period of this study
- Subjects who experienced serious adverse reactions
- Subjects who experienced serious adverse reactions after booster (third) vaccination
- Subjects who experienced serious adverse events
- Subjects who experienced non-serious adverse events
- Information about COVID-19 in subjects who experienced serious adverse events of COVID-19
- Subjects who experienced serious adverse events after booster (third) vaccination
- Subjects excluded from the safety analysis set who experienced serious adverse reactions
- Information about COVID-19 cases occurring after booster (third) vaccination
- Excluded data in subjects lacking information on booster (third) vaccination
- Details of reason for discontinuation in subjects who discontinued before booster (third) vaccination

Documents required for application of re-examination (of which forms are presented in PSEHB/PED Notification No. 1128-2 issued by the Director of the Pharmaceutical Evaluation Division, Pharmaceutical Safety and Environmental Health Bureau, Ministry of Health, Labour and Welfare dated November 28, 2017) will also be prepared.

[figure not shown]
In addition, documents required for the periodic safety reporting (of which forms are presented in PSEHB/PED Notification No. 1128-5 issued jointly by the Director of the Pharmaceutical Evaluation Division and the Director of the Safety Division, Pharmaceutical Safety and Environmental Health Bureau, MHLW dated November 28, 2017) will be prepared for the purpose of the reporting.

11. APPENDICES

11.1. Appendix 1: Example of Tables and Figures of Risk Ratios for Adverse Reactions Occurring in Subgroups

| Event name: Increased XXX | Category 1 | Category 2 | Risk Ratio (RR) | |
|---|---------------|---------------|-----------------|--------------|
| | n/N (%) | n/N (%) | RR | 95% CI |
| Sex (male vs. female) | 18/2220 (0.8) | 3/1099 (0.3) | 2.97 | (0.88-10.06) |
| Age (≥ 65 yrs. vs. < 65 yrs.) | 19/2788 (0.7) | 2/531 (0.4) | 1.81 | (0.42-7.74) |
| Diagnosis (disease A vs. disease B) | 3/221 (1.4) | 18/3098 (0.6) | 2.34 | (0.69-7.87) |
| Duration of disease (< 1 yr. vs. ≥ 1 yr.) | 9/771 (1.2) | 7/866 (0.8) | 1.44 | (0.54-3.86) |
| Concomitant use of Drug A (present vs. absent) | 9/798 (1.1) | 12/2521 (0.5) | 2.37 | (1.00-5.60) |
| Pretreatment with Drug A (present vs. absent) | 1/148 (0.7) | 20/3171 (0.6) | 1.07 | (0.14-7.93) |
| Complication of Disease B (present vs. absent) | 16/1614 (1.0) | 5/1703 (0.3) | 3.38 | (1.24-9.20) |
| Past history of Disease B (present vs. absent) | 7/674 (1.0) | 14/2643 (0.5) | 1.96 | (0.79-4.84) |
| Hepatic impairment (present vs. absent) | 0/80 | 18/2056 (0.9) | | |
| Renal impairment (present vs. absent) | 1/140 (0.7) | 17/2004 (0.8) | 0.84 | (0.11-6.28) |

Incidence Proportions and Risk Ratios for Adverse Reaction XXXX

● Category 1 VS. ▲ Category 2
